## 10.10. Pharmacokinetic Analysis (MEDI4736)

Individual MEDI4736 concentrations will be tabulated by dose cohort along with descriptive statistics. Individual and mean concentration-time profiles will be generated and included in the report. Pharmacokinetic parameters will be determined using standard non-compartmental methods. The following pharmacokinetics parameters will be determined after the first or steady-state dose: Peak concentration ( $C_{max}$ ), trough concentration ( $C_{trough}$ ), time to peak concentration ( $T_{max}$ ) and area under the curve (AUC), as data allow. Accumulation to steady

state will be assessed as the ratio of  $C_{max,ss}:C_{max}$  and  $C_{trough,ss}:C_{trough}$ . Descriptive statistics of non-compartmental pharmacokinetics parameters will be provided.

### **10.11. Immunogenicity Analyses**

Immunogenicity analyses will be performed by determining the anti-MEDI4736 response before and/or after treatment with ibrutinib and MEDI4736 at selected time points during treatment with ibrutinib and MEDI4736.

### **10.12. Pharmacodynamic Analyses**

Pharmacodynamic studies will be conducted to monitor both ibrutinib and MEDI4736 activity when co-administered. Blood samples will be collected at baseline and at selected time points during treatment with ibrutinib and/or MEDI4736. Pharmacodynamic assays for ibrutinib may include occupancy assays of ITK or other targets in the blood or other relevant assays such as pITK/pPLCgamma in PBMCs. To monitor the activity of MEDI4736 after ibrutinib treatment, sPD-L1 will be evaluated at selected time points.

### **10.13. Biomarker Analyses**

Clinically relevant biomarkers may be associated with clinical responses. Changes in phenotypic, genetic/genomic and molecular biomarkers may be evaluated over the course of ibrutinib and MEDI4736 treatment and will be summarized by treatment cohort. Association between baseline levels and changes from baseline in selected biomarkers and their response to treatment will be explored.

- Immune-cell subsets in peripheral blood will be evaluated by immunophenotyping.
- Secreted protein levels (ie, chemokines, cytokines) in serum or plasma will be evaluated.
- Tumor biopsies will be evaluated for key target expression (eg, PD-L1) via IHC, and genomic analyses may be performed if there is sufficient material for analysis; other biomarkers that predict sensitivity or resistance to the drug combination may also be explored.

## **11. ADVERSE EVENT REPORTING**

Timely, accurate, and complete reporting and analysis of safety information from clinical studies are crucial for the protection of subjects, investigators, and the Sponsor, and are mandated by regulatory agencies worldwide. The Sponsor has established Standard Operating Procedures in conformity with regulatory requirements worldwide to ensure appropriate reporting of safety information; all clinical studies conducted by the Sponsor or its affiliates will be conducted in accordance with those procedures.

## 11.1. Definitions

### 11.1.1. Adverse Events (AE)

An AE is any untoward medical occurrence in a subject administered a pharmaceutical product and which does not necessarily have a causal relationship with this treatment. An AE can therefore be any unfavorable and unintended sign (including a clinically significant abnormal laboratory finding, for example), symptom, or disease temporally associated with the use of an investigational study drug, whether or not considered related to the study drug ([ICH-E2A, 1995](#)).

For the purposes of this clinical study, AEs include events which are either new or represent detectable exacerbations of pre-existing conditions.

The term “disease progression” should not be reported as an adverse event term. As an example, “worsening of underlying disease” or the clinical diagnosis that is associated with disease progression should be reported.

Adverse events may include, but are not limited to:

- Subjective or objective symptoms provided by the subject and/or observed by the Investigator or study staff including laboratory abnormalities of clinical significance.
- Any AEs experienced by the subject through the completion of final study procedures.
- AEs not previously observed in the subject that emerge during the protocol-specified AE reporting period, including signs or symptoms associated with the underlying disease that were not present before the AE reporting period.
- Complications that occur as a result of protocol-mandated interventions (eg, invasive procedures such as biopsies).

The following are NOT considered AEs:

- **Pre-existing condition:** A pre-existing condition (documented on the medical history CRF) is not considered an AE, unless the severity, frequency, or character of the event worsens during the study period.
- **Pre-planned or elective hospitalization:** A hospitalization planned before signing the informed consent form is not considered an SAE, but rather a therapeutic intervention. However, if during the pre-planned hospitalization an event occurs, which prolongs the hospitalization or meets any other SAE criteria, the event will be considered an SAE. Surgeries or interventions that were under consideration, but not performed before enrollment in the study, will not be considered serious if they are performed after enrollment in the study for a condition that has not changed from its baseline level. Elective hospitalizations for social reasons, solely for the administration of chemotherapy, or due to long travel distances, are also not SAEs.
- **Diagnostic Testing and Procedures:** Testing and procedures should not be reported as AEs or SAEs, but rather the cause for the test or procedure should be reported.

### 11.1.2. Serious Adverse Events

A serious adverse event based on ICH and EU Guidelines on Pharmacovigilance for Medicinal Products for Human Use is any untoward medical occurrence that at any dose:

- Results in death (ie, the AE actually causes or leads to death).
- Is life-threatening. Life-threatening is defined as an AE in which the subject was at risk of death at the time of the event. It does not refer to an event which hypothetically might have caused death if it were more severe. If either the Investigator or the Sponsor believes that an AE meets the definition of life-threatening, it will be considered life-threatening.
- Requires in-patient hospitalization >24 hours or prolongation of existing hospitalization.
- Results in persistent or significant disability/incapacity (ie, the AE results in substantial disruption of the subject's ability to conduct normal life functions).
- Is a congenital anomaly/birth defect.
- Is an important medical event that may not result in death, be immediately life-threatening or require hospitalization, but may be considered an SAE when, based upon appropriate medical judgment, the event may jeopardize the subject or the subject may require intervention to prevent one of the other outcomes listed in this definition. Examples of such events are intensive treatment in an emergency department or at home for allergic bronchospasm, blood dyscrasias, or convulsion that does not result in hospitalization; or development of drug dependency or drug abuse.

Given that the Investigator's perspective may be informed by having actually observed the event, and the Sponsor is likely to have broader knowledge of the drug and its effects to inform its evaluation of the significance of the event, if either the Sponsor or the Investigator believes that the event is serious, the event will be considered serious.

### 11.1.3. Severity Criteria (Grade 1-5)

Definitions found in the [CTCAE v4.03](#) will be used for grading the severity (intensity) of AEs. The [CTCAE v4.03](#) displays Grades 1 through 5 with unique clinical descriptions of severity for each referenced AE. Should a subject experience any AE not listed in the [CTCAE v4.03](#), the following grading system should be used to assess severity:

- Grade 1 (Mild AE) – experiences which are usually transient, requiring no special treatment, and not interfering with the subject's daily activities
- Grade 2 (Moderate AE) – experiences which introduce some level of inconvenience or concern to the subject, and which may interfere with daily activities, but are usually ameliorated by simple therapeutic measures
- Grade 3 (Severe AE) – experiences which are unacceptable or intolerable, significantly interrupt the subject's usual daily activity, and require systemic drug therapy or other treatment

- Grade 4 (Life-threatening or disabling AE) – experiences which cause the subject to be in imminent danger of death
- Grade 5 (Death related to AE) – experiences which result in subject death

#### **11.1.4. Causality (Attribution)**

The Investigator is to assess the causal relation (ie, whether there is a reasonable possibility that the study drug caused the event) using the following definitions:

Not Related:	Another cause of the AE is more plausible; a temporal sequence cannot be established with the onset of the AE and administration of the investigational product; or, a causal relationship is considered biologically implausible.
Unlikely:	The current knowledge or information about the AE indicates that a relationship to the investigational product is unlikely.
Possibly Related:	There is a clinically plausible time sequence between onset of the AE and administration of the investigational product, but the AE could also be attributed to concurrent or underlying disease, or the use of other drugs or procedures. Possibly related should be used when the investigational product is one of several biologically plausible AE causes.
Related:	The AE is clearly related to use of the investigational product.

#### **11.2. Unexpected Adverse Events**

An “unexpected” AE is an AE that is not listed in the Investigator's Brochure/package insert or is not listed at the specificity or severity that has been observed. For example, hepatic necrosis would be “unexpected” (by virtue of greater severity) if the Investigator's Brochure referred only to elevated hepatic enzymes or hepatitis. Similarly, cerebral thromboembolism and cerebral vasculitis would be “unexpected” (by virtue of greater specificity) if the Investigator's Brochure/package insert listed only cerebral vascular accidents. “Unexpected” also refers to AEs that are mentioned in the Investigator's Brochure as occurring with a class of drugs or as anticipated from the pharmacological properties of the drug, but are not specifically mentioned as occurring with the study drug under investigation.

#### **11.3. Special Reporting Situations**

Special reporting situations on a Sponsor study that may require expedited reporting and/or safety evaluation include, but are not limited to:

- Overdose of any study drug
- Suspected abuse/misuse of a study drug
- Inadvertent or accidental exposure to a study drug

- Medication error involving a product (with or without subject exposure to the study drug, eg, name confusion)

Occurrence of any special reporting situations should be recorded in the eCRF. If any special reporting situation meets the criteria of an adverse event, it should be recorded on the adverse events eCRF. If the adverse event is considered serious, it should be recorded on the adverse events eCRF as serious and should be reported on the Serious Adverse Event Report Form. The SAE Report Form should be sent via email or fax to Pharmacyclics Drug Safety or designee within 24 hours of awareness.

## **11.4. Documenting and Reporting of Adverse Events and Serious Adverse Events by Investigators**

### **11.4.1. Assessment of Adverse Events**

Investigators will assess the occurrence of adverse events and serious adverse events at all subject evaluation time points during the study. All adverse events and serious adverse events whether volunteered by the subject, discovered by study personnel during questioning, detected through physical examination, clinically significant laboratory test, or other means, will be recorded in the subject's medical record and on the Adverse Event CRF and, when applicable, on the Serious Adverse Event Report Form.

Each recorded adverse event or serious adverse event will be described by its duration (ie, start and end dates), severity, regulatory seriousness criteria (if applicable), suspected relationship to the investigational product, and any actions taken.

### **11.4.2. Adverse Event Reporting Period**

All AEs, whether serious or non-serious, will be documented in the source documents from the time the signed and dated ICF is obtained until 30 days following the last dose for ibrutinib and/or 90 days after the last dose for MEDI4736. SAEs will be reported to the Sponsor from the time of ICF signing. Non-serious AEs will be recorded in the eCRF from the first dose of study drug until 30 days after the last dose of ibrutinib and/or 90 days after the last dose of MEDI4736. If both study drugs were discontinued at the same time, an SAE after 30 days and up to 90 days from the last dose of study drugs should indicate the causality for MEDI4736 only and N/A for ibrutinib (unless there is a causal relationship to ibrutinib).

Serious adverse events reported after 30 days following the last dose of ibrutinib and/or 90 days after the last dose of MEDI4736 should also be reported if considered related to any of the study drugs.

Progressive disease should NOT be reported as an event term, but instead symptoms/clinical signs of disease progression may be reported (see [Section 11.1.1](#)).

All adverse events, regardless of seriousness, severity, or presumed relationship to study drug, must be recorded using medical terminology in the source document. All records will need to capture the details of the duration and the severity of each episode, the action taken with respect to the study drug, the Investigator's evaluation of its relationship to the study drug, and the event outcome. Whenever possible, diagnoses should be given when signs and symptoms are due to a common etiology (eg, cough, runny nose, sneezing, sore throat, and head congestion should be reported as "upper respiratory infection"). Investigators must record in the CRF their opinion concerning the relationship of the adverse event to study therapy. All measures required for adverse event management must be recorded in the source document and reported according to Sponsor instructions.

All deaths should be reported with the primary cause of death as the AE term, as death is typically the outcome of the event, not the event itself. Autopsy and postmortem reports must be forwarded to the Sponsor, or designee, as outlined above, if allowed per local regulatory guidelines.

If a death occurs within 30 days after the last dose of ibrutinib and/or 90 days after the last dose of MEDI4736, the death must be reported to the Sponsor as a serious adverse event.

#### **11.4.3. Expediting Reporting Requirements for Serious Adverse Events**

All serious adverse events (initial and follow-up information) will be reported on the Serious Adverse Event Report Form and sent via email or fax to Pharmacyclics Drug Safety, or designee, within 24 hours of the discovery of the event or information. Pharmacyclics may request follow-up and other additional information from the Investigator (eg, hospital admission/discharge notes and laboratory results). The contact information (phone, email and fax) for Pharmacyclics Drug Safety can be found on the Serious Adverse Event Report Form and instructions.

All serious adverse events that have not resolved by the end of the study, or that have not resolved upon discontinuation of the subject's participation in the study, must be followed until any of the following occurs:

- The event resolves
- The event stabilizes
- The event returns to baseline, if a baseline value/status is available
- The event can be attributed to agents other than the study drug or to factors unrelated to study conduct
- It becomes unlikely that any additional information can be obtained (subject or health care practitioner refusal to provide additional information, lost to follow-up after demonstration of due diligence with follow-up efforts)

The Sponsor assumes responsibility for appropriate reporting of AEs to the regulatory authorities and governing bodies according to local regulations.

The Investigator (or Sponsor where required) must report these events to the appropriate Independent Ethics Committee/Institutional Review Board (IEC/IRB) that approved the protocol unless otherwise required and documented by the IEC/IRB.

#### **11.4.4. Pregnancy**

Before study enrollment, subjects must agree to take appropriate measures to avoid pregnancy. However, should a pregnancy occur in a female study subject, consent to provide follow-up information regarding the outcome of the pregnancy and the health of the infant until 30 days old will be requested.

A female subject must immediately inform the Investigator if she becomes pregnant from the time of consent to 90 days after the last dose of study drug. A male subject must immediately inform the Investigator if his partner becomes pregnant from the time of consent to 90 days after the last dose of study drug. Any female subjects receiving study drug(s) who become pregnant must immediately discontinue study drug. The Investigator should counsel the subject, discussing any risks of continuing the pregnancy and any possible effects on the fetus.

Although pregnancy itself is not regarded as an adverse event, the outcome will need to be documented. Any pregnancy occurring in a subject or subject's partner from the time of consent to 90 days after the last dose of study drug must be reported. Any occurrence of pregnancy must be recorded on the Pregnancy Report Form Part I and sent via email or fax to Pharmacyclics Drug Safety, or designee, within 24 hours of learning of the event. All pregnancies will be followed for outcome, which is defined as elective termination of the pregnancy, miscarriage, or delivery of the fetus. For pregnancies with an outcome of live birth, the newborn infant will be followed until 30 days old by completing the Pregnancy Report Form Part II. Any congenital anomaly/birth defect noted in the infant must be reported as a serious adverse event.

#### **11.4.5. Other Malignancies**

All new malignant tumors including solid tumors, skin malignancies and hematologic malignancies will be reported for the duration of study treatment and during any protocol-specified follow-up periods including post-progression follow-up for overall survival. Other malignancies will only be reported as an SAE if the event meets any serious adverse event reporting requirement listed under section "Serious Adverse Event" (otherwise captured as an AE in the eCRF).

#### **11.4.6. Adverse Events of Special Interest (AESI)**

Specific adverse events, or groups of adverse events, will be followed as part of standard safety monitoring activities by the Sponsor. These events (regardless of seriousness) should be reported on the Serious Adverse Event Report Form and sent via email or fax to Pharmacyclics Drug Safety, or designee, within 24 hours of awareness.

#### **11.4.6.1. Major Hemorrhage**

Major hemorrhage is defined as any of the following:

- Any treatment-emergent hemorrhagic adverse event of Grade 3 or higher\*.
- Any Treatment-emergent serious adverse event of bleeding of any grade.
- Any Treatment-emergent central nervous system hemorrhage/hematoma of any grade.

\*All hemorrhagic events requiring transfusion of red blood cells should be reported as Grade 3 or higher AE per [CTCAE v4.03](#).

Events meeting the definition of major hemorrhage will be captured as an event of special interest according to [Section 11.4.6](#) above.

#### **11.4.6.2. Pneumonitis**

Pneumonitis has been reported in association with use of anti-PD-L1/anti-PD-1 antibodies ([Brahmer 2012](#)). Initial work-up should include a high-resolution CT scan, ruling out infection, and pulse oximetry. Additional assessments are to include pulmonary function tests and blood gases. Pulmonary consultation is recommended.

For Grade 2 pneumonitis that does not resolve to Grade <1 within 3 days of maximal supportive care (including corticosteroids) or Grade  $\geq 3$  pneumonitis, permanently discontinue MEDI4736.

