**Study D4191C00003/ATLANTIC:** The safety profile of durvalumab monotherapy in Study CD-ON-durvalumab-1108 is generally consistent with that of Study D4191C00003/ATLANTIC in subjects with locally advanced or metastatic non-small-cell lung cancer (NSCLC) treated with durvalumab 10 mg/kg Q2W. As of 05 May 2015, 264 of 303 subjects (87.1%) reported any AE in Study D4191C00003/ATLANTIC. Overall, events reported in  $\geq 10\%$  of subjects were dyspnea (18.8%), fatigue (17.8%), decreased appetite (17.5%), cough (14.2%), pyrexia (12.2%), asthenia (11.9%), and nausea (11.2%). Nearly two-thirds of the subjects experienced AEs that were Grade 1 or 2 in severity and manageable by general treatment guidelines as described in the current durvalumab study protocols. Grade 3 or higher AEs were reported in 107 of 303 subjects (35.3%). A total of 128 subjects (42.2%) reported AEs that were considered by the investigator as related to investigational product. Treatment-related AEs (all grades) reported in  $\geq 2\%$  of subjects were decreased appetite (6.6%); fatigue (5.9%); asthenia (5.0%); nausea (4.6%); pruritus (4.3%); diarrhea, hyperthyroidism, hypothyroidism, and pyrexia (3.3% each); rash (2.6%); weight decreased (2.3%); and vomiting (2.0%). Treatment-related Grade 3 AEs reported in  $\geq 2$  subjects were pneumonitis (3 subjects) and increased GGT (2 subjects). There was no treatment-related Grade 4 or 5 AEs. Ninety-four of 303 subjects (31.0%) reported any SAE. SAEs that occurred in  $\geq 1.0\%$  of subjects were dyspnea (6.6%); pleural effusion, general physical health deterioration (2.3% each); pneumonia (2.0%); hemoptysis, pulmonary embolism (1.3% each); and pneumonitis, respiratory failure, disease progression (1.0% each). Nine subjects had an SAE considered by the investigator as related to durvalumab. Each treatment-related SAE occurred in 1 subject each with the exception

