	Grade 1 (Asymptomatic , clinical or diagnostic observations only, intervention not indicated)	No dose modification required. However, consider holding study drug/study regimen dosing as clinically appropriate and during diagnostic work-up for other etiologies	For Grade 1 (Radiographic Changes Only): 
 
Monitor and closely follow up in 2-4 days for clinical symptoms, pulse oximetry (resting and exertion) and laboratory work-up and then as clinically indicated
 
Consider pulmonary and infectious disease consult
 

	Grade 2 (Symptomatic, medical intervention indicated, limiting instrumental	Hold study drug/study regimen dose until Grade 2 resolution to Grade $\leq 1$ 
 
If toxicity worsens then treat as Grade 3 or Grade 4
 
	For Grade 2 (Mild to Moderate New Symptoms): 
 
Monitor symptoms daily and consider hospitalization
 
Promptly start systemic steroids (e.g., prednisone 1-2 mg/kg/day or IV equivalent)
 
Reimaging as clinically indicated
 
If no improvement within 3-5 days, additional
 

Immune-Mediated Reactions			
	Dose Modifications	Toxicity Management	
	ADL)	
 
If toxicity improves to baseline then the decision to reinitiate study drug/regimen at next scheduled treatment date will be based upon treating physician's clinical judgment.
 
Study drug/study treatment can be resumed at the next scheduled dose once event stabilizes to Grade <math>\leq 1</math> and 5-7 days have passed after completion of steroid taper
 
	

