### **5.6. Criteria for Permanent Discontinuation of Study Drug**

Investigators are encouraged to keep a subject who is experiencing clinical benefit in the study unless significant toxicity puts the subject at risk or routine noncompliance puts the study outcomes at risk. For a complete list of criteria for permanent discontinuation of study treatment, refer to [Section 9.2](#).

Subjects who withdraw for any reason other than those specified in [Section 5.3](#) and [9.2](#) will not be replaced. A Treatment Termination Visit ([Section 8.2.3](#)) and End-of-Treatment Visit ([Section 8.3.1](#)) are required for all subjects except for those subjects who have withdrawn full consent.

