### **6.1. Permitted Concomitant Medications**

Supportive medications in accordance with standard practice (such as for emesis, diarrhea, etc.) are permitted. Use of neutrophil growth factors (filgrastim and pegfilgrastim) or red blood cell growth factors (erythropoietin) is permitted per institutional policy and in accordance with ASCO guidelines ([Smith 2006](#)). Transfusions may be given in accordance with institutional policy.

Hormonal or bone sparing treatment are permitted with approval of the Medical Monitor.

Short courses ( $\leq 14$  days) of corticosteroid treatment for non-cancer related medical reasons considered unrelated to study treatment (eg, unrelated joint inflammation, asthma exacerbation, rash, antiemetic use and infusion reactions) at doses that do not exceed 100 mg per day of prednisone or equivalent are permitted after discussion with the Medical Monitor. During corticosteroid treatment with  $>10$  mg per day of prednisone or equivalent, MEDI4736 should be held until event resolution to Grade  $\leq 1$  or baseline; thereafter MEDI4736 administration may be resumed at the next scheduled dose. Doses higher than this are permitted only for infusion prophylaxis/reactions or for acute toxicity management.

If corticosteroid treatment for study drug related adverse events with  $>10$  mg per day of prednisone or equivalent is needed, MEDI4736 should be held until the event resolves to Grade  $\leq 1$  or baseline and the Medical Monitor should be contacted. Thereafter, MEDI4736

administration may be resumed at the next scheduled dose (also see [Section 5.5.2.4](#) for Dose Modifications for Adverse Reactions).

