#### **9.2. Withdrawal from Study Treatment**

Study treatment will be discontinued in the event of any of the following events:

- Progressive disease
- Unacceptable toxicity: an intercurrent illness or adverse event that prevents further administration of ibrutinib and/or MEDI4736
- Symptomatic deterioration
- Dose-Limiting Toxicity
- Withdrawal of consent for treatment by subject
- Investigator decision (such as chronic noncompliance, significant protocol deviation, or best interest of the subject)
- Lost to follow-up
- Study termination by Sponsor
- Subject becomes pregnant

All subjects, regardless of reason for discontinuation of study treatment will undergo a Treatment Termination and an End-of-Treatment Visit and be followed for progression and survival.

*The Investigator should notify the Sponsor within 24 hours if a subject discontinues ibrutinib and/or MEDI4736 treatment due to PD, a DLT, or an AE and should provide redacted documentation of disease progression for review by the Sponsor's Medical Monitor.*

If a subject shows signs of disease progression on physical examination or laboratory assessment, the subject may continue study treatment until disease progression is confirmed. These subjects should stay in the study to be followed for survival.

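### Section 11.4.6.2 orders a permanent stop of MEDI4736 for Grade 2 pneumonitis not cleared in 3 days; the readable dosing text allows restart with no such limit, and nothing says which governs

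*Protocol*

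**What the plan says.** **Protocol 11.4.6.2 (Pneumonitis, under adverse events of special interest).** MEDI4736 is permanently discontinued "For Grade 2 pneumonitis that does not resolve to Grade <1 within 3 days of maximal supportive care", where that care includes corticosteroids, and also for pneumonitis of Grade 3 or higher.

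**Protocol 5.5.2.4 (toxicity table, pneumonitis row, Grade 2).** The dose-modification column says to hold until Grade ≤1. On return to baseline, restart is left to the treating physician. Otherwise treatment can resume at the next scheduled dose once the event is Grade ≤1 and "5-7 days have passed after completion of steroid taper". Permanent discontinuation appears in this row only for Grades 3 and 4. The toxicity-management column starts steroids at 1–2 mg/kg/day prednisone and breaks off in the available text at "If no improvement within 3-5 days, additional".

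**Protocol 5.5.2.4 (general row).** Two further permanent-stop conditions apply: steroids that cannot be reduced to 10 mg/day or less within 12 weeks, and recurrence of a Grade 3 treatment-related event.

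**Protocol 6.1.** If a drug-related event needs more than 10 mg/day of prednisone, MEDI4736 is held until Grade ≤1 or baseline "and the Medical Monitor should be contacted. Thereafter, MEDI4736" may be resumed. The section refers the reader to 5.5.2.4.

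**Protocol 5.6 and 9.2.** Section 5.6 sends the reader to 9.2 with the words "For a complete list of criteria for permanent discontinuation of study treatment". The only toxicity entry in 9.2 is general: "Unacceptable toxicity: an intercurrent illness or adverse event that prevents further administration of ibrutinib and/or MEDI4736".

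**Protocol 11.4.6.** Of the special-interest events it says "These events (regardless of seriousness) should be reported", to the sponsor's drug safety group within 24 hours.

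**The concern.** Two parts of one protocol tell the investigator what to do with MEDI4736 after Grade 2 pneumonitis, and they do not agree. One is a mandatory permanent stop with a 3-day clock. The other is a hold with permission to restart. They also use different recovery grades: below 1 in 11.4.6.2, and 1 or below in 5.5.2.4 and 6.1.

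An error can go either way. A site working from the dosing sections could re-dose a subject whom 11.4.6.2 says must stop. If the sponsor meant the 5.5.2.4 rule, a site applying 11.4.6.2 would end a subject's MEDI4736 irrevocably, because Protocol 3.1 bars re-treatment after permanent discontinuation. Sites that read the sections differently would also add avoidable variation to MEDI4736 exposure and to counts of discontinuation for adverse events. Protocol 1.4.5 says there are no clinical data on the combination in these tumors, so the rule cannot be dismissed as one that will never be used.

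**Working it through.** **Step 1: the same subject under each text.** Take Grade 2 pneumonitis treated with steroids, and classify it by its state on day 3 of maximal supportive care.

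| State on day 3 | 11.4.6.2 | 5.5.2.4 dose-modification column and 6.1 | Agree? |
|---|---|---|---|
| Grade 0 | No permanent stop | May resume when the restart conditions are met | Yes |
| Grade 1, still Grade 1 after taper | Permanent stop if the threshold is <1; no stop if ≤1 was meant | May resume | Only if ≤1 was meant |
| Grade 2, later Grade ≤1 | Permanent stop on either reading | May resume | No |
| Worsened to Grade 3 or 4 | Permanent stop | Permanent stop (5.5.2.4) | Yes |

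The third line is the firm part, because it does not depend on how the recovery grade is read. The second depends on one symbol.

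**Step 2: does another rule supply the limit?** The two general conditions in 5.5.2.4 concern a 12-week steroid taper and recurrent Grade 3 events. Neither amounts to a 3-day limit for Grade 2 pneumonitis. Section 6.1 has no time limit for the event itself. None of 5.5.2.4, 5.6, 6.1 and 9.2 refers to 11.4.6.2, 11.4.6.2 does not refer back, and no text ranks them.

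**Step 3: how many subjects?** The protocol gives no pneumonitis rate for the combination. The 303-subject NSCLC monotherapy study in Protocol 1.5.3 gives a bound:

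- The list of treatment-related events at 2% or more includes vomiting at 2.0%. Since 6/303 = 1.98% and 7/303 = 2.31%, that is 6 subjects.
- Pneumonitis is not on the list, so at most 5 subjects had it as treatment-related (5/303 = 1.65%).
- Three had it at Grade 3, and there were no treatment-related Grade 4 or 5 events. That leaves at most 5 − 3 = 2 at Grades 1–2.
- 2/303 = 0.66%, with exact (Clopper-Pearson) 95% interval 0.08% to 2.36%.
- For about 130 Phase 2 subjects: 130 × 0.66% = 0.86, with interval 0.10 to 3.07. At 0.66%, the chance of at least one case is 1 − (1 − 0.0066)^130 = 0.58.

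These figures cover monotherapy and treatment-related events only. They pool Grades 1 and 2 and do not yet require failure at 3 days, which would lower them. A higher rate on the combination would raise them. As an assumption only, a combination rate of 1% to 5% would give 130 × 0.01 = 1.3 to 130 × 0.05 = 6.5 subjects, again before requiring Grade 2 and failure at 3 days.

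**Step 4: the consequence for an affected subject.** Under 11.4.6.2 no further MEDI4736 is given. Under 5.5.2.4 the subject may receive whatever remains of the 26-dose maximum (Protocol 1.8.3) after the hold and taper, for as long as other stopping criteria are not met.

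**The case against.** The strongest reply is that the texts differ in force. Section 11.4.6.2 is an instruction, whereas the 5.5.2.4 guidelines are framed as recommendations and their restart wording is permissive. A site can satisfy both by applying the stricter rule. This stands, and it means that compliance with both is possible. It helps only a site that has found 11.4.6.2, and it does not show which rule the sponsor intended.

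Second, the sponsor would usually know in time. The steroid dose for Grade 2 pneumonitis exceeds 10 mg/day, so 6.1 brings in the Medical Monitor, and special-interest events are reported within 24 hours. This is real mitigation. It still leaves the sponsor's own reviewer without a stated rule.

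Third, a reader might infer that the 3-day rule is absent from 5.5.2.4 altogether. The documents do not support that, because the Grade 2 toxicity-management cell is cut off just after a day count. The matching Grade 3–4 cell continues with further work-up and immunosuppression, so the lost text may well do the same, but that is inference. The difference is shown only for the dose-modification column.

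Fourth, a reader might take the silence of 9.2, after 5.6 calls it complete, as evidence that the rule was dropped. It is weak evidence: 9.2 also omits the other event-specific stops in 5.5.2.4, such as Grade 3–4 pneumonitis and diarrhea. Nor is a dosing rule in Section 11 odd in itself, since 11.4.6.3 contains one for infusion reactions.

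**Conclusion.** The point holds in a limited form. For Grade 2 pneumonitis, 11.4.6.2 sets a 3-day permanent-stop rule for MEDI4736. The readable dose-modification column of 5.5.2.4 and Section 6.1 permit resumption at Grade ≤1 with no such limit, and nothing ranks them. The instructions are opposite for a subject who is Grade 2 on day 3 and later recovers. For a subject who is Grade 1 on day 3, they conflict only if Grade <1 is meant literally. Grades 3 and 4 are handled consistently.

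The likely size is about one subject or fewer per 130. That rests on carrying over treatment-related monotherapy data, and the combination rate is unknown. The matter is one of subject safety and of consistent MEDI4736 exposure and discontinuation data. It should not be read as touching the efficacy conclusions: Grade 2 pneumonitis is not a DLT by the Protocol 5.3 definition, and the ORR analysis and sample size do not depend on this rule. It should be fixed because it is a safety stop rule and the correction is only wording.

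**What to change.** State one Grade 2 pneumonitis rule for MEDI4736 in the 5.5.2.4 pneumonitis row, with a single time limit and a single recovery grade chosen by the sponsor. By default, keep the 3-day permanent-stop rule and confirm whether Grade <1 or Grade ≤1 is meant. If the sponsor does not want the limit, remove it from 11.4.6.2. In either case, replace the dosing sentence in 11.4.6.2 with a cross-reference to the 5.5.2.4 row, and add a pneumonitis exception to the resumption rule in 6.1. While editing, check the full Grade 2 toxicity-management cell against the chosen rule.

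Any interim clarification letter must use the same time limit and recovery grade as the amendment. Otherwise a subject at Grade 1 on day 3 could be stopped under the letter yet be allowed to resume once the amendment takes effect.

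The cost is wording in three sections at the next amendment and, if used, one letter to sites. Sample size and analyses do not change.
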